### ***3.4 Additional Endpoints***

Additional analysis of data collected may be performed and reported.

## **4 STATISTICAL ANALYSIS**

### ***4.1 General Approach***

**Continuous Outcomes.** Continuous outcomes will be summarized with mean, standard deviation and other relevant statistically summaries. When not normally distributed, medians and quantiles will be reported. A confidence interval approach may be used, if appropriate, to compare outcomes with historical information. Repeated measures analysis of variance may be used for outcomes assessed multiple times over the course of follow-up.

**Binary Outcomes.** Binary and ordinal outcomes will be tabulated. Rates will be expressed as a percentage taking into account denominators as listed above. If required, confidence intervals for proportions will be calculated using the exact binomial distribution. A confidence interval approach may be used to compare outcomes with historical information. Comparisons of proportions will be done with chi-squared or Fisher's exact test. Multivariate analysis may also be performed.

### ***4.2 Primary Endpoint Calculation and Sample Size Determination***

Prior studies have shown that IPSS scores are reduced by approximately 16 points after Aquablation, values similar to those observed after TURP. In patients with moderate-to-severe BPH, the mean change in IPSS score representing slight improvement is approximately 5 points. Therefore, showing a mean reduction in IPSS scores that statistically exceeds  $16-5 = 11$  points will be interpreted as study success. The study's primary endpoint hypothesis is a one-way statistical test (alpha=.025 for interpretation):

$$\begin{aligned} H_0: \text{Mean(IPSS change score at 3 months)} &\leq 11 \\ H_a: \text{Mean(IPSS change score at 3 months)} &> 11 \end{aligned}$$

With 100 patients and assuming 10% subjects lost to follow, 90 evaluable subjects with an underlying change of 16 points and a change score SD of 7.5 points yields a 99% power to detect an improvement of more than 11 points.

The WATER study (IDE#G150089) used an assumption that a TURP rate for the same safety definition provided in this protocol would be 65% for a range of prostate sizes 30-80mL. The same safety target will be used for this protocol treating large prostates of 80-150mL. The assumed true rate for the Aquablation patients will be 50% (10% greater than WATER in order to account for treating larger prostates). The study's primary endpoint hypothesis is a one-way statistical test (alpha=.025 for interpretation):

$$\begin{aligned} H_0: \text{Mean (safety rate at 3 months)} &\geq 65\% \\ H_a: \text{Mean (safety rate at 3 months)} &< 65\% \end{aligned}$$

The primary safety endpoint with 90 evaluable subjects has an 80% power to detect a safety rate of less than 65%.

## **5 RISK/BENEFIT ANALYSIS**

The study protocol has been designed to provide the greatest benefits while assuring the safety of participating subjects by mitigating the occurrence, limiting the severity, and ameliorating the effects of any possible adverse events. The following describes the benefits subjects will receive as well as possible adverse events which have been identified as risks and for which subjects will be carefully monitored.

### ***5.1 Potential Benefits***

The primary potential benefit of participation is the potential occurrence of successful treatment of lower urinary tract symptoms using the AQUABEAM System. Additional benefits may be decreased post-operative duration of pain, decreased need for urinary catheter postoperatively, and faster overall recovery. In a patient with urinary retention, the need for catheter use (indwelling or intermittent) may be reduced.

### ***5.2 Potential Risks***

The AQUABEAM System is used during a surgical procedure on the lower urinary tract. Risks associated with surgical procedures, some of which could be fatal, include:

- Irritative symptoms of urgency, hesitancy, dysuria, and nocturia
- Bleeding
- Lower urinary tract infection
- Bladder, rectum, or prostate injury
- Reaction to anesthesia
- Sphincter damage
- Urinary extravasation
- Swelling or irritation of the prostate, bladder, perineum, or urethra
- Pain
- Changes in ejaculatory function
- Reproductive system disturbances
- Blood Transfusion
- Perforation

### **5.3 Risk Mitigation**

Risks during study participation will be minimized by the following:

- The study protocol was developed in concert with the study's principal investigator, who is well-known in the area of BPH treatment
- The site was chosen because of proven expertise in the field of urological surgery
- The investigator will receive specific training and instruction in the use of the AQUABEAM System
- Study subjects undergo intensive monitoring throughout the study by a multidisciplinary team
- Pre-clinical, in vitro, and in vivo testing has been performed in order to optimize the device safety and function
- Clinical testing in previous human subjects has been performed in order to optimize the device safety and function

## **6 STUDY ADMINISTRATION**

### **6.1 Clinical Events Committee**

An independent Clinical Events Committee (CEC), consisting of three physicians who are not study Investigators will be utilized for this trial. This CEC will be responsible for the review and adjudication of reported adverse events up to 12 months related to the device or the procedure that occur over the course of the study per the CEC Charter. Additionally, the CEC may adjudicate other events at the request of the Data Monitoring Committee or Sponsor. The CEC adjudicators shall classify (assign relatedness) the above described adverse events based on severity and association to the procedure or other attribution.

Device- or procedure-related events which are associated with the secondary safety endpoint analysis will be as adjudicated by the CEC. In the event the CEC differs from the Investigator in classification of events, the resulting CEC adjudication will be used for final analysis and reporting.

A CEC Charter will be developed prior to the start of study enrollment. The CEC Charter shall include consistent definitions for each type of event and shall outline the review process.

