## **2.20 Adverse events**

The occurrence of all adverse events will be documented in all study subjects throughout the study treatment and 12 months follow-up period. Only urological SAEs and urological events will be collected at 24 months, 36 months, 48 months, and 60 months follow-up visits. AE information (start and stop date, description of event, severity, relatedness to the treatment procedure, the device itself or other study-related procedures) will be assessed and recorded on CRFs. Whether an AE meets the definition for serious adverse event will be determined by the study investigator using **Table 3**. All urological events consistent with a SAE must be reported to the Sponsor within 24 hours of awareness of the event. Relatedness of the AE to the surgical procedure or the study device itself will be judged by the clinical events committee (CEC) for adverse events up to 12 months according to **Table 4**.

The classification of surgical complications shall be done per **Table 5** by the CEC. Note that persistent ejaculatory or erectile dysfunction, the need for re-catheterization after postoperative day 3, and urinary incontinence related to surgery are considered to be surgical complications.

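### Protocol 6.1 conflicts with Protocol 2.20 and SAP 5.2 on which events and which endpoint the CEC adjudicates, leaving events the site calls unrelated without an assured route to review

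*Protocol*

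**What the plan says.** **Which events.** Protocol 6.1 gives the CEC "review and adjudication of reported adverse events up to 12 months related to the device or the procedure". The next sentence reads: "Additionally, the CEC may adjudicate other events at the request of the Data Monitoring Committee or Sponsor". The committee's task is then set out: "The CEC adjudicators shall classify (assign relatedness) the above described adverse events based on severity and association to the procedure or other attribution".

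Protocol 2.20 is wider. Relatedness to the procedure or device "will be judged by the clinical events committee (CEC) for adverse events up to 12 months", using Table 4, which runs from unrelated to definitely related. Nothing in 2.20 restricts this to events already thought related. The same section has the CEC grade surgical complications by Clavien-Dindo (Table 5).

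**Which endpoint.** Protocol 6.1 says: "Device- or procedure-related events which are associated with the secondary safety endpoint analysis will be as adjudicated by the CEC". It does not name the primary safety endpoint. SAP 5.2 states that the CEC adjudicates the primary safety endpoint. SAP 6.2 uses CEC relatedness for the secondary ejaculatory/erectile dysfunction endpoint and allows for the CEC finding an event unrelated.

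**Whose ruling counts.** Protocol 6.1 ends the matter without limiting it to any endpoint: "In the event the CEC differs from the Investigator in classification of events, the resulting CEC adjudication will be used for final analysis and reporting".

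**The concern.** The primary safety endpoint (Protocol 3.2, SAP 5.2) counts a subject only if an event is rated probably or definitely related and is Grade 2 or higher, or is Grade 1 with persistent disability. The relatedness rating therefore decides who enters the numerator. The trial has one arm, so every assessor knows the treatment, and the rate is tested against a fixed 65%. A loss of endpoint subjects has no matching loss in a control group to offset it.

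Followed literally, 6.1 selects events for review by the property the committee is meant to judge. An event that the site wrongly rates unrelated then has no mandatory route to the CEC. The only other route is a request from the data monitoring committee (DMC) or the sponsor. Two teams following 6.1 and 2.20 respectively could send different sets of events to the CEC and arrive at different primary rates.

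**Working it through.** **Step 1: the passages side by side.**

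| Question | Protocol 6.1 | Protocol 2.20 | SAP |
|---|---|---|---|
| Events reviewed routinely, to 12 months | Those related to device or procedure | Adverse events, no pre-selection | Not stated; 6.2 expects some CEC findings of unrelated |
| Other events | Optional, at DMC or sponsor request | Not mentioned | Not mentioned |
| Endpoint that uses CEC rulings | A secondary safety endpoint | Not stated | 5.2: primary safety; 6.2: secondary ejaculatory/erectile |
| CEC overrides the investigator | Yes, any classification | Relatedness and grade are the CEC's | 5.2: the CEC adjudicates the endpoint |

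Protocol 6.1 does not say who makes the initial relatedness call or what level triggers referral. That the site makes it is an inference from two places: 2.20 has relatedness recorded on the case report forms, and 6.1 provides for the CEC differing from the investigator.

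**Step 2: the plan's own figure.** The inputs from Protocol 4.2 and SAP 5.2 are a target of 65%, an assumed true rate of 50%, one-sided alpha 0.025, 90 evaluable subjects, an exact binomial test and a stated power of 80%.

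- Critical value: the largest c with P[Bin(90, 0.65) ≤ c] ≤ 0.025. At c = 49 the probability is 0.0248; at c = 50 it is 0.0401. Success is therefore 49 or fewer of 90 (54.4%).
- Exact power: P[Bin(90, 0.50) ≤ 49] = 82.9%.
- Normal approximations: 83.6% with the null variance in the critical value, 81.2% with the alternative variance throughout, and 80.8% with the null variance and a continuity correction.

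The stated 80% is reproduced and is not in question.

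**Step 3: boundary for the 101 treated men (Protocol 2.11).** P[Bin(101, 0.65) ≤ 55] = 0.0184 and P[Bin(101, 0.65) ≤ 56] = 0.0296. Success is 55 or fewer of 101 (54.5%).

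**Step 4: sensitivity to missed subjects (illustration).** Let m be the share of true endpoint subjects who are never referred to the CEC and so are not counted. The documents give no value for m. At a true rate of 65% the counted rate is 0.65 × (1 − m), and the chance of passing is P[Bin(n, 0.65(1 − m)) ≤ c].

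| m (assumed) | Counted rate | n = 90, c = 49 | n = 101, c = 55 |
|---|---|---|---|
| 0% | 65.0% | 2.5% | 1.8% |
| 2% | 63.7% | 4.4% | 3.5% |
| 5% | 61.75% | 9.5% | 8.1% |
| 10% | 58.5% | 24.9% | 23.4% |
| 20% | 52.0% | 71.5% | 72.3% |

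Here m is a share of subjects, not of events: a man with two qualifying events still counts if one of them is referred. The model allows for no upgrades among referred events.

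**The case against.** A reader might infer from 6.1 that adjudication can only lower the primary safety rate. The documents do not support that. Among the events it receives, the CEC assigns relatedness and, under 2.20, the Clavien-Dindo grade. It can move an event from possible to probably related, or from Grade 1 to Grade 2, and either can add an endpoint subject. Its ruling replaces the investigator's in both directions. Only the selection step before review works one way.

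The filter reading itself can be contested. Protocol 6.1 tells the CEC to assign relatedness, which suggests the question is still open when an event arrives. The sentence on other events does not settle it: those could be events after 12 months, since urological events are collected to 60 months. It only adds events, gives the sponsor no power to withhold any, and is also open to the DMC, which is independent and receives adverse event reports. The CEC Charter, which sets out the review process, is not among the documents and may already require referral of everything.

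Nor does the label secondary safety endpoint show that 6.1 excludes the primary. No endpoint carries that name, but the ejaculatory/erectile endpoint is a plausible referent. In that case 6.1 is silent on the primary, and SAP 5.2 covers it.

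These points narrow the concern without removing it. The scope in 6.1 is narrower than in 2.20, its wording on endpoints does not match SAP 5.2, and the override sentence helps only for events that reach the committee.

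**Conclusion.** There is an inconsistency to resolve: Protocol 6.1 disagrees with Protocol 2.20 on which events the CEC reviews, and with SAP 5.2 on which endpoint its rulings serve. If 6.1 is applied as a filter on the site's rating, events wrongly called unrelated have no assured route to correction, and that step favours meeting the 65% target.

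The documents cannot show that such a bias occurred, or how large it would be. The rise from 1.8% to 8.1% or 23.4% (101 men) assumes that 5% or 10% of true endpoint subjects were never referred and that no upgrades offset this. It shows that the test is sensitive to small losses; it does not estimate the error in this trial. The sample size, alpha and stated power are unaffected. The point should be acted on because the relatedness rating decides the primary safety result and the correction is cheap.

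**What to change.** 1. Reword Protocol 6.1 so that the CEC reviews all reported adverse events up to 12 months, regardless of the investigator's relatedness rating, and assigns relatedness by Table 4 and Clavien-Dindo grade by Table 5. This matches 2.20. Align the CEC Charter.
2. In 6.1, replace the reference to a secondary safety endpoint with the primary safety endpoint and the secondary ejaculatory/erectile dysfunction endpoint. Both must be named, because SAP 6.2 relies on CEC rulings for the second.
3. The 101 men have already been treated, so rewording alone is not enough. Before the primary safety analysis, confirm that every reported event through 3 months has been through the CEC, including those the site rated unrelated, and send any that have not.

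The cost is protocol and charter wording and somewhat more events for the existing committee to review. No new data collection is needed, and the test and sample size stay as they are.

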### **6.2 Data Monitoring Committee**

The Data Monitoring Committee (DMC) will consist of a minimum of three (3) members and this group shall also act as the steering committee chartered with advising the sponsor on the design and execution of the study, monitoring the overall implementation of the study, including subject enrollment, protocol compliance, and reviewing the final primary endpoint analysis (3 months follow-up).

Membership will include only independent members and therefore will not include a study investigator or a representative from the sponsor. The DMC meetings will consist of open and closed sessions (i.e. "open" denotes sponsor staff present; "closed" denotes without sponsor staff present).

The sponsor or designate will provide the DMC with reports related to subject enrollment, procedural outcome, follow-up visits, adverse events, and any other material the DMC may deem necessary to carry out its responsibilities as established at the outset of the committee in the DMC charter. The DMC will assess if early evidence exists for dramatic benefit or harm for subjects while the clinical study is in progress. The DMC will make recommendations to the sponsor concerning continuation, modification, or termination of the study.

The DMC will establish and maintain a Charter detailing specific operating procedures. Names and contact information for all DMC members will be on-file at the sponsor and available on request.

### ***6.3 Data Collection/Electronic Case Report Forms (e-CRF)***

Case report forms will be used to collect all subject data during the study within the EDC system and are referred to as eCRFs. The EDC system enables rapid data acquisition and cleaning through extensive data checking and query processing. Monitor visits will be conducted in regular intervals through the study based upon site enrollment rates.

Data will be entered into a secure EDC system, which allows 21 CFR Part 11 compliance. Subjects' follow up visits data will be entered directly by the site with corresponding source documents maintained at the site level.

### ***6.4 Clinical Monitoring***

The study will be monitored to ensure that applicable regulations are followed. Written procedures will be established by PROCEPT BioRobotics or their authorized designee to ensure the quality of the study and to ensure that each person involved in the monitoring process carries out the required duties.

Prior to subject enrollment, a study initiation visit will be completed at each investigational site to ensure the following:

- IRB approval has been obtained and documented
- The Investigators and study personnel are appropriately trained and clearly understand the study
- The Investigators and study personnel accept the obligations incurred in undertaking this clinical investigation.

Periodic monitoring visits will be made at all active study sites throughout the clinical study to assure that the Investigator obligations are fulfilled and all applicable regulations and guidelines are followed. These visits will assure that the facilities are still acceptable, the protocol and investigational plan are being followed, the IRB has been notified of approved protocol changes as required, complete records are being maintained, appropriate and timely reports have been made to the Sponsor and the IRB, device and device inventory are controlled, and the Investigator is carrying out all agreed activities.

A study termination visit will be conducted at the completion of the clinical investigation to ensure that all subject data are properly documented and that all clinical materials are returned to PROCEPT BioRobotics.

If a clinical monitor becomes aware that an Investigator is not complying with the signed Investigator's Agreement, the Investigational Plan, the requirements of Investigational Device Exemption regulations (21 CFR 812), or any conditions of approval imposed by the IRB, PROCEPT BioRobotics will either secure compliance or discontinue shipments of the device to the Investigator and terminate the Investigator's participation in the investigation.

## 7 STUDY REPORT AND PUBLICATION STRATEGY

### 7.1 *Final Study Report*

A Final Study Report will be prepared by PROCEPT BioRobotics.

### 7.2 *Publication Strategy*

The study will be registered with a clinical trials database, as recommended by the International Committee of Medical Journal Editors.

The Principal Investigator agrees to provide copies of any and all proposed manuscripts to PROCEPT BioRobotics at least 30 days in advance of submitting such proposed manuscripts to a publisher or other third party to evaluate the proposed manuscript for the following purposes:

- For accuracy and consonance with the study database,
- To ascertain whether confidential information or other proprietary information of PROCEPT BioRobotics (including trade secrets and patent protected materials) is being inappropriately utilized and/or released,
- To provide Principal Investigator with information which may not yet be available to them, and
- To provide input from other Investigators and Co-Investigators in the study, if any, regarding the content and conclusions of the proposed manuscripts.

For the avoidance of doubt, PROCEPT BioRobotics may not require any amendments to be made to the clinical data, omissions to be made to it or amendments to the Principal Investigator's interpretation thereof. The decision as to whether to amend the manuscript to include any or all of the opinions or information provided by PROCEPT BioRobotics remains that of the Principal Investigator.

If PROCEPT BioRobotics makes a good faith determination, within such 30-day period, that the publication or presentation would be detrimental to its intellectual property interests, the Principal Investigator shall refrain from submitting such proposed manuscript to a publisher or other third party for another 365 days or such earlier time that notifies PROCEPT BioRobotics to allow time to file PROCEPT BioRobotics patent applications or take other steps to protect its intellectual property interests.

### **1 BACKGROUND**

WATER II is a prospective multicenter trial of Aquablation using AQUABEAM system for men with symptomatic benign prostatic hyperplasia (BPH) and large prostates (80-150 g). See clinical investigational protocol TP0124 for details regarding eligibility, treatments and assessments. This document describes the study's statistical analysis plan (SAP).

This study is related to WATER (TP0038) in that the same device is used on men with the same condition. The major difference is that WATER II targets men with larger prostates and does not have a concurrent control group.

The purpose of WATER II is to determine safety and efficacy in the target population.

### **2 ELECTRONIC DATA CAPTURE**

PROCEPT is using “iMedNet” (MedNet Solutions, Minnetonka, MN 55305) as the electronic data capture provider. iMedNet is a fully functional, 21 CFR 11-compliant web-based system for managing case report forms and downloading study-related data.

### **3 DATA ANALYSIS SOFTWARE**

Statistical analysis will be done using R,\* an open source data analysis package.

### **4 ANALYSIS COHORTS**

The following analytic cohorts are defined.

#### **4.1 Modified Intent-to-Treat (mITT) Cohort**

The mITT population includes all enrolled subjects in whom the Aquablation handpiece is inserted into the penile urethra. A patient found at the time of the procedure to have a condition that results in study exclusion does not contribute to the mITT cohort. The mITT population is the primary analysis population for both the primary safety and effectiveness endpoints.

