**Figure 4 AQUABEAM Console**  
(Refer to User Manual for current configuration of the Console)

- ***AQUABEAM HANDPIECE***

The AQUABEAM Handpiece (**Figure 5**) is a sterile single use component of the AQUABEAM System. It obtains its power source and functional commands from the Motorpack. The AQUABEAM Handpiece is compatible with the AQUABEAM Scope, which is inserted into the central lumen of the Handpiece, enabling live cystoscopic visualization of the prostatic urethra and bladder during insertion and Aquablation treatment.

The tip of the Handpiece is inserted transurethral into the subject and advanced through the prostatic urethra into the bladder. Using both live TRUS and cystoscopic guidance, the operating physician positions the tip of the Handpiece to the desired location. Upon initiation of Aquablation treatment, the high-pressure sterile saline stream exits the AQUABEAM Handpiece tip at a 90° angle to the target prostatic tissue. The depth and angle of resection is based on the transferred planned contour and profile from the CPU to the Console.

[figure not shown]

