## 2.11 Sample Size

One hundred and one (101) participants who received study treatment under protocol rev. A.

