#### **4.2 Per-protocol (PP) Cohort**

The per-protocol (PP) population is all mITT subjects who:

1. meet critical study eligibility criteria;
2. have no significant protocol deviations that could affect the validity of data; and
3. have evaluable assessment for the endpoint of interest.

A significant protocol deviation means non-adherence on the part of the subject or investigator to clinically significant protocol-specific inclusion/exclusion criteria, primary objective variable criteria or critical study requirements that could affect the scientific validity of the observed data point or lead to bias. Missing data are not imputed for analyses with the PP cohort.

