#### **4.3 Safety Cohort**

The safety analysis population includes all subjects in whom Aquablation is initiated. This cohort is used for most safety analyses.

---

\* See <https://cran.r-project.org/>

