## 5.2 Primary Safety Endpoint

The study's primary safety endpoint is the proportion of subjects with adverse events rated as probably or definitely related to the study procedure classified as Clavien-Dindo Grade 2 or higher or any Grade 1 event resulting in persistent disability (e.g. incontinence, ejaculatory disorder, or erectile dysfunction) evidenced through 3 months post treatment. Note that the Clavien-Dindo classification scheme is for grading postoperative complications, not events that reflect lack of treatment efficacy. The endpoint is adjudicated by the study's clinical events committee (CEC).

The study's primary endpoint hypothesis is a one-way statistical test (alpha=.025 for interpretation):

$$\begin{aligned}
 H_0: \text{Mean (safety rate at 3 months)} &\geq 65\% \\
 H_a: \text{Mean (safety rate at 3 months)} &< 65\%
 \end{aligned}$$

An exact binomial test (binom.test in R) will be used to determine the P-value for the above comparison. Power calculations showed that the primary safety endpoint with 90 evaluable subjects has an 80% power to detect a safety rate of less than 65%.

The primary safety endpoint is calculated using the mITT population.

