## **7 ADDITIONAL ENDPOINT ASSESSMENTS**

Additional exploratory statistical analysis will be done using standard statistical methods. Analyses of interest are:

1. Proportion/rate of all Clavien-Dindo classifications at month 3.
2. Changes in the following ratings across all time points: IPSS, IPSS-QOL, Incontinence Severity Index (ISI), IIEF-15, MSHQ-EjD, pelvic pain intensity score, dysuria frequency and intensity score, and uroflow measures. For this and other repeated assessments, repeated measures analysis of variance may be used to calculate change from baseline. Semi-quantitative comparisons will be made to results from WATER.
3. Relationship between baseline IPSS and IPSS change scores.
4. Duration of bladder catheterization.
5. Whether discharged home with a bladder catheter.
6. Change in hemoglobin from preoperative to postoperative. Additional analysis will be performed to see if prostate size, anesthesia type, number of Aquablation passes, and intravesical median lobes were predictors of bleeding loss.
7. Reoperation rate at 1 year for lack of efficacy. (This endpoint excludes reoperation for complications.)
8. Change in proportion of subjects using BPH medications (e.g., alpha blockers, alpha-reductase inhibitors).
9. Prostate size reduction from baseline to 3 months as measured TRUS. A t test will be used for the comparison.
10. Relationship between prostate size and procedure or resection times. Linear or other models will be used to explore relationships.
11. Proportion of subjects with device- or procedure-related adverse event.
12. Proportion of subjects in whom re-catheterization was needed between discharge after the index procedure and month 3. Re-catheterization is defined as the need to place a urinary catheter in the bladder for symptoms related to BPH (primarily inability to urinate). This excludes re-catheterization for study purposes or for purposes unrelated to LUTS.
13. Amount of irrigation fluid used intraoperatively (liters). A t test or Wilcoxon's test will be used to compare to values from WATER.

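### As worded, the mITT rule can drop a man from the primary safety test after the handpiece has been inserted

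*SAP*

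**What the plan says.** SAP 4.1 makes insertion of the handpiece into the urethra the entry point to mITT. It then provides that a patient "found at the time of the procedure to have a condition that results in study exclusion does not contribute to the mITT cohort", and names mITT as the primary population for both primary endpoints. SAP 5.2 repeats this for safety: "The primary safety endpoint is calculated using the mITT population". That test compares the 3-month event rate with 65%, using an exact binomial test at one-sided 0.025.

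The other two cohorts do not restore a removed man to this test:

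- SAP 4.3: "The safety analysis population includes all subjects in whom Aquablation is initiated". It has no removal rule and serves the bulk of the safety analyses, but it is not assigned to the primary safety endpoint.
- SAP 4.2: "The per-protocol (PP) population is all mITT subjects who" meet further conditions. A man outside mITT is therefore outside PP too.

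On size, SAP 5.2 states that "the primary safety endpoint with 90 evaluable subjects has an 80% power", and Protocol 2.11 gives "One hundred and one (101) participants who received study treatment under protocol rev. A".

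**The concern.** A cohort that begins at exposure normally keeps everyone exposed, above all for safety. Here the entry rule and the removal sentence meet awkwardly. A man who never had the handpiece inserted is not in mITT to begin with, so the only men whose membership the sentence can change are men already inserted.

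Discovery after insertion is possible. Protocol 2.4 describes the scope inside the handpiece as "enabling live cystoscopic visualization of the prostatic urethra and bladder during insertion and Aquablation treatment". Several exclusion criteria in Protocol Table 1, such as stricture, bladder calculus or suspected bladder cancer, concern what that view could show.

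The study has one arm and a fixed target, so no control group absorbs an exclusion of this kind. If exposed men leave the denominator, the rate set against 65% is no longer the rate among men exposed to the device. SAP 4.1 does not list the qualifying conditions or say who decides.

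**Working it through.** **Inputs.** Null rate 65%, one-sided alpha 0.025, exact binomial test, 90 evaluable men (SAP 5.2). Assumed true rate 50% (Protocol 4.2). Treated number 101 (Protocol 2.11). The number of removed men is not given, so it is an assumption here and is varied from one to three.

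**The plan's own figure.** Normal approximation with continuity correction, n=90:

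Φ[(0.65 − 0.50 − 1/180 − 1.96·√(0.65·0.35/90)) / √(0.50·0.50/90)] = Φ[(0.1500 − 0.0056 − 0.0985)/0.0527] = Φ(0.871) = 80.8%.

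This matches the stated 80%. The exact test passes at 49 or fewer events of 90 (attained alpha 0.0248) and has 82.9% power. The stated power is sound, and the point does not depend on it.

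**Who can be affected.**

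| Man | mITT | Safety Cohort | PP |
|---|---|---|---|
| Not inserted | out already | out | out |
| Inserted, excluding condition found, not ablated | removed | out | out |
| Inserted, excluding condition found, ablated | removed | in | out |

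Only the last two rows are changed by the removal sentence. The second row belongs to no defined cohort.

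**Size away from the cut-off.** Start at 45/90 = 50.0%.

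- Removing one, two or three men with events gives 44/89 = 49.4%, 43/88 = 48.9%, 42/87 = 48.3%.
- Removing event-free men gives 45/89 = 50.6%, 45/88 = 51.1%, 45/87 = 51.7%.

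That is about 0.5 to 0.6 points per man, in either direction.

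**Size at the cut-off.** p = P(X ≤ x | n, 0.65); the test passes if p ≤ 0.025. The removed or restored men all have events, except in the last two rows.

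| Assumption | Sequence | Men needed to change the decision |
|---|---|---|
| 90 is the full inserted set | 50/90 (0.0401, fail), 49/89 (0.0333, fail), 48/88 (0.0274, fail), 47/87 (0.0224, pass) | 3 removed |
| 90 is the set after removal | 49/90 (0.0248, pass), 50/91 (0.0302, fail) | 1 restored |
| 101 is the full inserted set | 56/101 (0.0296, fail), 55/100 (0.0246, pass) | 1 removed |
| 101 is the set after removal | 55/101 (0.0184, pass), 56/102 (0.0223, pass), 57/103 (0.0269, fail) | 2 restored |
| 90 is the full set, removed man event-free | 49/90 (0.0248, pass), 49/89 (0.0333, fail) | 1 removed |
| 101 is the full set, removed men event-free | 55/101 (0.0184, pass), 55/100 (0.0246, pass), 55/99 (0.0326, fail) | 2 removed |

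Because the exact test is discrete, the count needed depends on n. A single removed man with an event turns a fail into a pass at 8 of the 21 full-set sizes from 85 to 105.

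**How often the boundary is met.** At a true rate of 50%, the probability of the just-failing count is 4.8% for 50/90 and 4.4% for 56/101. A changed decision is less likely still, because the removals must also happen and carry the right outcomes.

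**The case against.** The sentence may have been written only for men found unsuitable before insertion, for instance at the treatment-day TRUS. It would then be redundant and harmless. That reading is fair and cannot be ruled out, but SAP 4.1 does not say so, and an analyst following the text would also remove inserted men.

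A reader might infer that men are dropped because of how they fared, or that removal is decided after exposure. The documents support neither. The SAP gives no decision time. The listed exclusions are largely pre-existing conditions, and a finding made at the procedure precedes most of the 3-month event window. Nor do the documents show that anyone was removed.

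The 101-man flip should not carry the argument alone. Protocol 2.11 counts men who received treatment, so a man inserted but never ablated would not normally be among them, and using 101 as the full set assumes no losses.

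The Safety Cohort is the natural default for the Clavien-Dindo tabulation and for the item "Proportion of subjects with device- or procedure-related adverse event" in SAP 7, although neither names a cohort. Events in ablated men would therefore probably still be reported. That is a real mitigation for disclosure, but those analyses do not feed the test against 65%.

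Finally, restoring men can help the device: one restored event-free man turns 56/101 (p=0.0296, fail) into 56/102 (p=0.0223, pass). This is a reason to show a sensitivity analysis. It does not justify keeping the removal.

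**Conclusion.** The point holds as a defect of wording with a possible effect on a primary endpoint. Read literally, SAP 4.1 and 5.2 together let an inserted man and his complications leave the primary safety rate, and no other provision returns him to that test.

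The effect is small: about half a percentage point per man, of unknown sign, for a number of men that may be zero. It changes the decision only near the cut-off of roughly 54% to 55%. With events in all the men concerned, that takes one to three men, depending on the denominator and on whether it is counted before or after removal. A conclusion that the primary safety result is biased in the device's favour would go beyond the documents. The change is still worth making, because it is cheap and takes post-exposure exclusions out of a single-arm safety rate.

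**What to change.** - In SAP 5.2, run the primary safety test on all enrolled men in whom the handpiece was inserted, without the SAP 4.1 removal. Alternatively, limit that removal in SAP 4.1 to conditions found before insertion. The two are equivalent for safety provided that a man found ineligible before insertion is not then inserted. The second also alters the effectiveness cohort.
- State how inserted men without 3-month safety data are counted. SAP 5.1 has imputation rules for IPSS but SAP 5.2 has none for safety, and an untreated man who exits under Protocol 2.24 may lack those data.
- Report the same exact test on the Safety Cohort as a sensitivity analysis, since inserted but never-ablated men could dilute the rate.
- List each man to whom the removal sentence would apply, with the reason and his adverse events.

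The cost is a few sentences in SAP 4.1 and 5.2, one extra run of the test and a short listing. Protocol 2.20 already calls for adverse events to be documented in all study subjects. The downside is that the rate may move slightly in either direction.
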